## 10.6. Appendix 6: Specific Criteria for the Inclusion of Potential Participants with Chronic Stable HIV, HCV, or HBV Infection

The following guidelines should be used to consider for inclusion potential participants with chronic stable HIV, HCV, or HBV infection. If a potential participant does not have relevant laboratory results pertaining to HIV infection in his/her medical records from the last 6 months before screening, they will be instructed to go to their local health care provider and obtain the necessary data for potential entry into the trial. Potential participants will not be screened for laboratory evidence of HIV, HCV, or HBV infection. For a potential participant with a medical history of HCV or HBV infection, the below guidelines regarding stable infection are intended to inform the investigator's judgment of eligibility, but the availability of all the listed laboratory data in the medical records is not mandatory.

### 1. Stable/well-controlled HIV infection includes:

- a. CD4 cell count  $\geq 300$  cells/ $\mu$ L.
- b. HIV viral load  $< 50$  copies/mL.
- c. Participant must be on stable anti-retroviral treatment (ART) for 6 months (unless the change is due to tolerability, in which case the regimen can be for only the previous 3 months; changes in formulation are allowed; nationwide guidelines that require transition from one ART regimen to another are allowed) and the participant must be willing to continue his/her ART throughout the study as directed by his/her local physician.

*Note: Participants with ongoing and progressive comorbidities associated with HIV infection will be excluded but comorbidities associated with HIV infection that have been clinically stable for the past 6 months are not an exclusion criterion.*

*Laboratory methods for confirming a diagnosis of HIV infection are: Any evidence (historic or current) from medical records, such as ELISA with confirmation with Western Blot or PCR, or of a detectable viral load (country-specific regulatory approved tests).*

### 2. Stable known HCV infection:

History of chronic HCV with evidence of sustained virological response (defined as undetectable HCV RNA) for  $\geq 12$  weeks following HCV treatment or without evidence of HCV RNA viremia (undetectable HCV viral load).

### 3. Stable known HBV infection:

May be defined as presence of hepatitis B surface antigen for  $\geq 6$  months and:

- a. HBeAg negative, anti-HBe positive, and/or
- b. Serum HBV DNA  $< 2,000$  IU/mL; and
- c. No other findings indicating active inflammatory process in liver.

**10.7. Appendix 7: Protocol Amendment History**

The Protocol Amendment Summary of Changes Table for the current amendment is located directly before the Table of Contents (TOC).

6.4. Appendix 4: Toxicity Grading Scale for Vital Signs.....	22
7. REFERENCES.....	23

VERSION HISTORY

Table 1: SAP Version History Summary

SAP Version	Approval Date	Change	Rationale
1.0	11 September 2023	Not Applicable	Initial release
2.0	21 May 2024	
(1) Added
 
 – MAAE to the safety analysis, – Non-inferiority testing based on MOPA functional titers at 29 days after the administration of ExPEC9V vaccine, – Description of the details and type of data to be reviewed by the IDMC. 
(2) Day 59 is removed from Table 6 (Visit Windows for HI Antibody Titers Immunogenicity Analysis).
 
(3) Data for the stratification factors, age and history of UTI will be obtained as collected from the eCRF; in addition, analysis using data from IWRS will be performed to support non-inferiority.
 
(4) Add ExPEC immunogenicity analysis stratified by baseline titer (titers \leq LLOQ and titers $>$ LLOQ).
 
(5) Minor changes (e.g., grammar, paragraph rearrangement) to the SAP for clarity.
	
(1) Requested by Health Authority.
 
(2) HI titer at Day 59 will not be available.
 
(3) Clarify the source of data for the stratification variables age and history of UTI, whether (as collected) from the eCRF or (as stratified) from IWRS.
 
(4) Interest in ExPEC immunogenicity analysis stratified by baseline immune status.

LIST OF ABBREVIATIONS

ADaM	Analysis Data Model
AE	adverse event
AS	All Screened
BMI	body mass index
CI	confidence interval
CoAd	Coadministration
CSP	clinical study protocol
E. coli	Escherichia coli
ECL	Electrochemiluminescent
eCRF	electronic case report form
EPA	exotoxin A derived from Pseudomonas aeruginosa
ExPEC9V	9-valent extraintestinal pathogenic Escherichia coli vaccine
FAS	full analysis set
GMR	geometric mean ratio
GMT	geometric mean titer
HD	high dose
HI	hemagglutination inhibition
IDMC	Independent Data Monitoring Committee
IWRS	interactive web response system
LLOQ	lower limit of quantification
MAAE	medically attended adverse event
MOPA	multiplex opsonophagocytic killing assay
PPEI	per protocol ExPEC immunogenicity
PPII	per protocol influenza immunogenicity
SAE	serious adverse event
SAP	Statistical Analysis Plan
ULOQ	upper limit of quantification
UTI	urinary tract infection

1. INTRODUCTION

This SAP contains the definitions of analysis sets, derived variables, and statistical methods that will be used to evaluate the reactogenicity, safety and immunogenicity analysis of the VAC52416BAC3002 (E.ngage) study. The specifications of individual tables, listings and figures to be generated in each analysis will be described in the Data Presentation Specifications document.

This SAP is developed in line with the CSP Amendment 1 approved on 22 September 2023.

1.1. Objectives and Endpoints

Refer to Section 3 of the CSP. The statistical hypotheses are described in Section 2 of this SAP.

1.2. Study Design

Refer to Section 4.1 of the CSP for details on the study design. Refer to section 6.3 of the CSP for details on randomization and stratification and procedures for maintaining the blind. The target vaccination day for each intervention group is given in Table 2.

Table 2: Target Vaccination Days of the Study Intervention Groups

Group Number	Group Name	Day 1	Day 30
1	CoAd	ExPEC9V + Influenza vaccine	Placebo
2	Control	Placebo + Influenza vaccine	ExPEC9V

Group number and group name may be interchangeably used in the SAP.

2. STATISTICAL HYPOTHESES

To demonstrate the non-inferiority of the humoral immune response to the 4 influenza vaccine strains after concomitant administration of ExPEC9V and a HD quadrivalent seasonal influenza vaccine versus the administration of a HD quadrivalent seasonal influenza vaccine administered alone

AND

to demonstrate the non-inferiority of the humoral immune response against the O-serotype antigens after concomitant administration of ExPEC9V and a HD quadrivalent seasonal influenza vaccine versus the administration of ExPEC9V administered alone.

The following hypotheses will be tested:

Null Hypothesis:

For at least 1 of the 4 influenza vaccine strains: the GMT of HI antibody titers against the considered vaccine strain, 29 days after concomitant administration of ExPEC9V and a HD quadrivalent seasonal influenza vaccine is inferior by at least 1.5-fold to the GMT 29 days after the administration of a HD quadrivalent seasonal influenza vaccine alone

OR

For at least 1 of the 9 O-serotype antigens: the GMT of antibody titers against the considered O serotype antigen 29 days after concomitant administration of ExPEC9V and a HD quadrivalent seasonal influenza vaccine is inferior by at least 1.5-fold to the GMT 29 days after the administration of ExPEC9V alone.

Alternative Hypothesis:

For each of the 4 influenza vaccine strains: the GMT of HI antibody titers 29 days after concomitant administration of ExPEC9V and a HD quadrivalent seasonal influenza vaccine is non-inferior to the GMT 29 days after the administration of a HD quadrivalent seasonal influenza vaccine alone, using a non-inferiority margin of 1.5, for the ratio $\text{GMT}_{\text{Control group}}/\text{GMT}_{\text{CoAd group}}$

AND

For each of the 9 O-serotype antigens: the GMT of antibody titers 29 days after concomitant administration of ExPEC9V and a HD quadrivalent seasonal influenza vaccine is non-inferior to the GMT 29 days after the administration of ExPEC9V alone, using a non-inferiority margin of 1.5, for the ratio $\text{GMT}_{\text{Control group}}/\text{GMT}_{\text{CoAd group}}$.

3. SAMPLE SIZE DETERMINATION

Refer to Section 9.2 of the CSP.

4. PARTICIPANT ANALYSIS SETS

The study intervention assignment will follow the as-treated principle. The analysis sets that will be used in the analysis are shown in [Table 3](#).

Table 3: Description of Analysis Sets

Analysis Sets	Description
AS Set	This analysis set will include all participants screened for the study regardless of whether they were screen failures or they were enrolled into the study. Rescreened participants are counted only once.
Randomized Set	This analysis set will include all participants who were randomized i.e., had a valid randomization issued by IWRS implemented in this study.
FAS	The analysis set will include all participants who received at least one study vaccination, regardless of the occurrence of protocol deviations and vaccine type (HD quadrivalent seasonal influenza vaccine, ExPEC9V, or placebo). All safety and participant information analyses will be based on the FAS.
PPII Set	This analysis set will include all randomized participants who received the first study vaccination (ExPEC9V in combination with a HD quadrivalent

Table 3: Description of Analysis Sets

Analysis Sets	Description
	
seasonal influenza vaccine for the CoAd group and a HD quadrivalent seasonal influenza vaccine alone for the Control group), and for whom immunogenicity data are available for at least one of the influenza strains in the vaccine. Samples taken after a participant experiences a major protocol deviation expected to impact the immunogenicity outcomes will be excluded from PPII analysis.
 
The primary analysis set for analyses related to influenza immunogenicity is the PPII Set. As a sensitivity analysis, key tables may also be based on the FAS.

PPEI Set	
This analysis set will include all randomized participants who received ExPEC9V in combination with a HD quadrivalent seasonal influenza vaccine for the CoAd group and ExPEC9V alone for the control group and for whom O-antigen immunogenicity data are available for at least one E. coli serotype. Samples taken after a participant experiences a major protocol deviation expected to impact the immunogenicity outcomes will be excluded from the PPEI analysis.
 
The primary analysis set for analyses related to O-antigen immunogenicity is the PPEI Set. As a sensitivity analysis, key tables may also be based on the FAS.

The list of major protocol deviations that would lead to elimination from the immunogenicity analysis will be specified in the Major Protocol Violation Criteria Document, which is established before the study starts and will be finalized before database lock and unblinding. See [Appendix 2](#) for more details.

5. STATISTICAL ANALYSES

5.1. General Considerations

The significance level (α) is 5% (2-sided). As both non-inferiority objectives should be demonstrated to have a successful study and as no interim analyses before the primary analysis are planned, no multiplicity adjustments are needed.

5.1.1. Study Phases

The immunogenicity baseline (or reference) value for the two groups is determined as follows. For CoAd group, the baseline value of the HI and ExPEC9V antibody titers will be the value of the last available assessment prior to the vaccination on Day 1. For the Control group, the baseline value for the HI and ExPEC9V antibody titers will be the value of the last available assessment prior to the vaccination on Day 1 and Day 30, respectively.

If a participant received at Day 1 both vaccinations but the start date-time of one of the vaccinations is not available in the clinical database, this date-time will be imputed with the date-time of the other vaccination.

The safety analysis will present all results by phase. Immunogenicity results will be presented per scheduled time point as appropriate. Listings may be shown per phase and time point.

Study day or relative day is defined as follows:

- Study Day = visit date – date of Day 1 + 1; if visit date \geq date of Day 1 (date of first vaccination).
- Study Day = visit date – date of Day 1; if visit date < date of Day 1 (date of first vaccination).

For ExPEC9V immunogenicity endpoints in the Control group, the day of the second vaccination will be considered as Day 1 in Post-dose 2.

5.1.2. Phase Definitions

The phases in the study will be constructed as follows (see [Table 4](#)).

Table 4: Phase Definitions

Phase	Phase #	Period	Period #	Interval	
				From	To
Screening	1			Date and time of signing the informed consent form	One minute prior to start of Post-dose 1 period
Regimen	2	Post-dose 1	1	Date and time of first vaccination	Minimum of: 
 a) 23:59 at the date of last contact (for early discontinuation) b) 23:59 at the database cut-off date for analysis conducted before the final analysis c) For participant that discontinues from the second vaccination: the maximum of (29 days after the first vaccination at 23:59, scheduled visit completed 29 days after first vaccination at 23:59) is used d) For participant where the scheduled Day 30 visit = day of 2nd dose: one minute prior to Post-dose 2 e) For participant where the scheduled Day 30 visit < day of 2nd dose: scheduled visit 29 days after first vaccination at 23:59

Table 4: Phase Definitions

Phase	Phase #	Period	Period #	Interval	
				From	To
Follow-up 1	3			Only for participant where scheduled Day 30 visit < day of 2 nd dose or participant who discontinues from 2 nd vaccination: one minute after Post-dose 1 period end	Only for participant where the scheduled Day 30 visit < day of 2 nd dose: one minute prior to Post-dose 2
					For participant that discontinues from the 2 nd vaccination: Minimum of: a) 23:59 at the date of last contact (for early discontinuation or participants that completed the study) b) 23:59 at the date of database cut-off date for analyses conducted before the final analysis
Regimen	2	Post-dose 2	2	Date and time of second vaccination	Minimum of: a) 23:59 at the date of last contact (for early discontinuation) b) 23:59 at the date of database cut-off date for analysis conducted before the final analysis c) Maximum of (29 days after the 2 nd vaccination at 23:59, scheduled visit completed 29 days after the 2 nd vaccination at 23:59)
Follow-up 2	4			One minute after Post-dose 2 period end	Minimum of: a) 23:59 at the date of last contact (for early discontinuation) b) 23:59 at the database cut-off date for analysis conducted before the final analysis

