
 
To compare seroprotection rates against the 4 influenza vaccine strains after the concomitant administration of ExPEC9V and a HD quadrivalent seasonal influenza vaccine versus the administration of a HD quadrivalent seasonal influenza vaccine alone.
 
	
 
Seroprotection is defined for each of the 4 influenza vaccine strains as HI titer <math>\geq 1:40</math> at 29 days after the administration of a HD quadrivalent seasonal influenza vaccine.
 

 
To assess the safety and reactogenicity of ExPEC9V when administered separately or concomitantly with a HD quadrivalent seasonal influenza vaccine
 
	
 
Solicited local (injection site) and systemic AEs for 14 days post each vaccination.
 
Unsolicited AEs for 29 days post each vaccination.
 
MAAEs collected from administration of the first vaccination until 6 months post last vaccination.
 
SAEs collected from the administration of the first vaccination until 6 months post last vaccination.
 

 
To evaluate the immunogenicity of ExPEC9V when administered separately or concomitantly with a HD quadrivalent seasonal influenza vaccine.
 
	
 
Antibody titers to vaccine O-serotype antigens and EPA as determined by multiplex ECL-based immunoassay on Days 1, 30, and 59.
 

Objectives	Endpoints

 
To further evaluate the immunogenicity of ExPEC9V when administered separately or concomitantly with a HD quadrivalent seasonal influenza vaccine.
 
	
 
Opsonophagocytic antibody titers to vaccine O-serotype antigens as determined by MOPA 29 days after administration of ExPEC9V.
 

 
To evaluate the immunogenicity of ExPEC9V between participants with a history of UTI to those without a UTI history.
 
	
 
Antibody titers to vaccine O-serotype antigens, in participants reporting a history of UTI at enrollment and participants without a UTI history at enrollment, as determined by multiplex ECL-based immunoassay 29 days after administration of ExPEC9V.
 

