#### **All Adverse Events**

AEs and special reporting situations, whether serious or non-serious, that are related to study procedures or that are related to non-investigational sponsor products will be reported from the time a signed and dated ICF is obtained until the end of the study/early withdrawal.

Clinically relevant medical events not meeting the above criteria and occurring between signing of ICF and moment of first vaccination will be collected on the Medical History eCRF page as pre-existing conditions.

Solicited AEs, collected through an eDiary, will be recorded for each vaccination from the time of vaccination until 14 days post-vaccination.

All unsolicited AEs and special reporting situations will be collected for each vaccination from the time of vaccination until 29 days post-vaccination. Unsolicited AEs with the onset date outside the timeframe defined above (>29 days after previous study vaccination), which are ongoing on the day of the subsequent vaccination, should be recorded as such.

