#### **Adverse Events**

The verbatim terms used in the eCRF by investigators to identify AEs will be coded using the Medical Dictionary for Regulatory Activities (MedDRA). Any AE occurring at or after the initial administration of study vaccination through the day of last dose plus 29 days is considered to be treatment emergent. All reported treatment-emergent AEs will be included in the analysis. For each AE, the percentage of participants who experience at least 1 occurrence of the given event will be summarized by vaccination group.

Summaries, listings, datasets, or participant narratives may be provided, as appropriate, for those participants who die, who discontinue vaccination due to an AE, who experience a MAAE, or who experience a severe or an SAE.

Summaries and/or listings may be provided separately for AEs with onset outside the above defined timeframe (ie, beyond 29 days post-vaccination).

Solicited local (at injection site) and systemic AEs will be summarized descriptively. The number and percentages of participants with at least one solicited local (at injection site) or systemic AE will be presented. The frequencies by vaccine group as well as frequencies according to severity

and duration will be described for solicited AEs. Frequencies of unsolicited AEs, separately for all and vaccination-related only, will be presented by System Organ Class and preferred term, while those of solicited AEs will be presented only by preferred term.

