5.6.1. Adverse Events

5.6.1.1. Definitions

Solicited AEs shown in the tables are extracted from the investigator assessment pages (Clinical Events) of the eCRF. All solicited AEs at the injection site (local) are considered related to the study vaccine administration.

For unsolicited AEs, only the AEs within the 29-day period following each vaccination will be presented in the safety tables except for MAAE and SAE which will be captured and tabulated in the outputs covering the whole study period.

The severity of the AEs will be classified as Grade 1 to 4. Solicited or unsolicited events that are graded less than Grade 1, are not considered as AE.

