5.6.1.3. Phase Allocation of Adverse Events

Step 1: Allocation of events to the periods:

As the analysis of solicited events will be based on the overall assessment of the investigators which is documented in the CE domain, the ADaM dataset will be based on the CE domain. Solicited events are allocated to the phases as described below, however they are always allocated to the respective Post-dose period and will never be attributed to the screening phase. Time of day is not considered while attributing solicited AEs to phases.

Unsolicited adverse events are allocated to periods based on their start date/time. If the start date/time of an event falls between (or on) the start and stop date/time of a period, the AE is attributed to that period (treatment-emergent principle).

- In case of partial start or stop dates (i.e., time and/or day and/or month and/or year missing), the events are allocated to the periods using the available partial information on start and end date; no imputation will be done. If, for instance, the AE start date only month and year are available, these data are compared to the month and year information of the periods. This rule may lead to multiplication of the event as a consequence of its assignment to multiple periods.

- In case of a completely missing end date, the date is imputed by the cut-off date of the analysis for participants still ongoing in the study, and by the end date of the last period for participants who discontinued or completed the trial. In case of a completely missing start date, the event is allocated to the first active treatment phase (Post-dose 1 period), except if the end date of the AE falls before the start of the first active treatment phase (Post-dose 1 period).

Step 2: Combination of Events:

Overlapping/consecutive events are defined as events of the same participant with the same preferred term which have at least 1 day overlap or for which the start date of an event is 1 day after the end date of the preceding event. Overlapping/consecutive events may be combined into one AE or not, according to the following rules:

- 1) If overlapping/consecutive events start in one of the following phases/periods - Screening or Follow-up (defined as non-active periods) - followed by an AE in - Post-dose period (defined as active period) - they are allocated to their respective phases/periods and are considered as separate events.

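### SAP Table 4 ends the unsolicited-AE periods at visit dates that conflict with the 29-day window set elsewhere, and the SAP does not say which rule governs

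*SAP*

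**What the plan says.** **The 29-day window.** Protocol Section 3 defines the endpoint as "Unsolicited AEs for 29 days post each vaccination". Protocol 8.3.1 limits collection in the same way: "All unsolicited AEs and special reporting situations will be collected for each vaccination from the time of vaccination until 29 days post-vaccination". It adds one exception: later events "which are ongoing on the day of the subsequent vaccination, should be recorded as such". SAP 5.6.1.1 says that, MAAEs and SAEs apart, "only the AEs within the 29-day period following each vaccination will be presented in the safety tables". SAP 5.6.1.2 treats onset beyond 29 days as outside the timeframe, for separate summaries or listings.

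**The period rules.** SAP 5.6.1.3 places an unsolicited AE by its onset: if onset lies within a period, "the AE is attributed to that period (treatment-emergent principle" applies. The periods are those of SAP 5.1.2, Table 4. Discontinuation and data cut-off aside, they end as follows:

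- Post-dose 2, rule c: the later of 29 days after dose 2 and the "scheduled visit completed 29 days after the 2 nd vaccination at 23:59".
- Post-dose 1, rule c (second vaccination discontinued): the later of 29 days after dose 1 and the Day 30 visit.
- Post-dose 1, rule d (dose 2 given at the Day 30 visit): one minute before dose 2.
- Post-dose 1, rule e (dose 2 given after the Day 30 visit): 23:59 on the day of that visit. The time from then to dose 2 is Follow-up 1.

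**A further definition.** Protocol 9.4.4 counts any AE from the initial vaccination "through the day of last dose plus 29 days is considered to be treatment emergent". That interval is continuous and includes the time between doses.

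**The concern.** Two rules decide which unsolicited AEs appear under which period, and they give different answers. An AE starting 33 days after dose 2, before a late Visit 5, belongs to Post-dose 2 by Table 4 but is outside the window by SAP 5.6.1.1 and by the protocol. An AE starting 27 days after dose 1 is inside the endpoint window. If the Day 30 visit took place at 24 days and dose 2 was delayed, Table 4 puts it in Follow-up 1. Two programmers could follow the SAP faithfully and produce different tables.

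Safety and reactogenicity of ExPEC9V given separately or together with influenza vaccine is a secondary objective. SAP 5.6 presents safety by phase, with participants in the phase as denominator rather than person-time, so the length of a period feeds directly into the percentages.

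**Working it through.** **Visit window.** The Schedule of Activities gives ±7 days for Visits 3 and 5. Day 30 ± 7 is Day 23 to Day 37, which matches the [23, 37] of SAP Tables 5 and 6. With vaccination on Day 1, the visit falls V = 22 to 36 days after the dose. Table 4 does not itself restrict the visit to this window, so 36 days is the limit only for in-window visits.

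**Period lengths for in-window visits**

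| Table 4 rule | Length | Range (days) | Against 29 days |
|---|---|---|---|
| Post-dose 2, c | max(29, V) | 29 to 36 | up to 7 too long |
| Post-dose 1, c | max(29, V) | 29 to 36 | up to 7 too long |
| Post-dose 1, e | V | 22 to 36 | up to 7 too short or too long |
| Post-dose 1, d | time to dose 2 (= V) | 22 to 36 | agrees with protocol 9.4.4 between doses |

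**The two ExPEC9V periods.** The CoAd group receives ExPEC9V at dose 1 and the Control group at dose 2, so a reader comparing ExPEC9V with and without influenza vaccine sets Post-dose 1 beside Post-dose 2. Take Post-dose 1 = V and Post-dose 2 = max(29, V), with the same visit timing in both.

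- Late visit (V > 29): both equal V, so there is no gap.
- Early visit (V < 29): Post-dose 1 is V and Post-dose 2 is 29, so the gap is 29 − V, at most 7 days.

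All of the gap therefore comes from early visits. If a 29-day limit is also applied, the lengths become min(29, V) and 29. Let f(d) be the probability of at least one AE in d days. For every V, f(max(29, V)) + f(min(29, V)) = f(V) + f(29), so f(max(29, V)) − f(V) = f(29) − f(min(29, V)). A 29-day limit leaves the gap exactly as it was.

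**Size, under stated assumptions.** The documents give neither a visit-time distribution nor a background rate. I assume whole-day offsets from −7 to +7, and a constant hazard giving a fraction r with an AE in 29 days: f(d) = 1 − (1 − r)^(d/29). For uniform offsets the mean of max(29, V) is 29 + (1 + 2 + … + 7)/15 = 29 + 28/15 = 30.9 days. The mean of min(29, V) is 29 − 28/15 = 27.1 days. The last three columns are the mean of f(29) − f(min(29, V)), in percentage points.

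| Offsets | Mean V | Mean max(29, V) | Mean min(29, V) | Gap, r = 15% | r = 20% | r = 25% |
|---|---|---|---|---|---|---|
| Uniform | 29.0 | 30.9 | 27.1 | 0.9 | 1.2 | 1.4 |
| Triangular | 29.0 | 30.3 | 27.7 | 0.6 | 0.8 | 1.0 |
| Normal, SD 2 | 29.0 | 29.8 | 28.2 | 0.4 | 0.5 | 0.6 |

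For r = 20% and uniform offsets, Table 4 alone gives 20.0% against 21.1%. With the 29-day limit it gives 18.8% against 20.0%. If every visit were 7 days early, f(22) = 1 − 0.8^(22/29) = 15.6% against 20.0%. If every visit were on target or 7 days late, the gap would be zero.

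**The case against.** The best defence is that the two SAP rules do different jobs: Table 4 allocates, and 5.6.1.1 then limits what is displayed. On that reading, onsets on days 30 to 36 never reach the safety tables. Collection also stops at 29 days, so what is recorded after that would be chiefly MAAEs, SAEs and events still ongoing at dose 2. This may be what was intended, and it would settle the long side. But the SAP does not say so, and 5.6.1.3 attaches the treatment-emergent label to the Table 4 period. The defence also does nothing for rule e, because a display limit cannot return to Post-dose 1 an event already allocated to Follow-up 1.

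It is also fair to say that rule d agrees with protocol 9.4.4, that both randomised groups follow the same rules within each period, that MAAEs and SAEs are tabulated over the whole study, and that SAP 5.6 rules out formal comparisons between groups. All of this stands and keeps the point modest.

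A reader might infer something stronger: that running to 36 days biases the ExPEC9V comparison in favour of co-administration, and that a 29-day cap would cure it. The documents do not support that. Late visits lengthen both periods alike, and the cap leaves the gap unchanged. Neither document names CoAd Post-dose 1 against Control Post-dose 2 as the main safety contrast.

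**Conclusion.** The inconsistency is real and should be resolved in the SAP. Post-dose 2 rule c and Post-dose 1 rule c can run past the 29-day endpoint and collection limit. Rule e can remove up to 7 days of the endpoint window from Post-dose 1. No sentence says which definition governs.

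The unequal length of the two ExPEC9V periods is a separate and smaller matter, caused by an early dose 2. Its size, about 0.4 to 1.4 percentage points, rests on assumed visit timing, the same timing in both periods, a constant hazard and a 15% to 25% background rate. It affects how a descriptive table reads. No hypothesis test, error rate or power depends on it.

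**What to change.** 1. In SAP Table 4, for unsolicited AEs, end Post-dose 2 (rule c) and Post-dose 1 (rules c and e) at 23:59 on vaccination day + 29 days, or one minute before dose 2 if that is earlier. Keep the existing limits for discontinuation and data cut-off.
2. State in SAP 5.6.1.1 and 5.6.1.3 that this is the one window used both for allocation and for display.
3. Leave rule d as it is, with Post-dose 1 ending at dose 2, in line with protocol 9.4.4, and apply the 29-day display limit of 5.6.1.1. Table 4 gives these participants no Follow-up 1, so no new phase is needed.
4. Wherever CoAd Post-dose 1 and Control Post-dose 2 are shown side by side, add a person-time rate or a common-window table, for example the first 22 days after ExPEC9V. This is needed because, after steps 1 to 3, an early dose 2 still leaves Post-dose 1 at 22 to 28 days against 29 days for Post-dose 2.

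The cost is SAP wording, one revised derivation and one extra table, with no new data. A few AEs with onset 30 to 36 days after a dose move to the follow-up summaries. Some of these are between-dose onsets that protocol 9.4.4 calls treatment-emergent, so the SAP should say how they are flagged. The whole-study MAAE and SAE tables do not change.
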